3.2 END OF STUDY AND LENGTH OF STUDY

The end of this study is defined as the time when all enrolled patients with FL and all enrolled patients with DLBCL have completed the 90-day safety follow-up visit, following completion or premature discontinuation of study treatment.

The total length of the study, from screening of the first patient to the end of the study, is expected to be approximately 4 years.

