5.6 ADVERSE EVENTS THAT OCCUR AFTER THE ADVERSE EVENT REPORTING PERIOD

After the end of the adverse event reporting period (defined as 90 days after the last dose of study treatment), all deaths, regardless of cause, should be reported through use of the Long-Term Survival Follow-Up eCRF.

In addition, if the investigator becomes aware of a serious adverse event that is believed to be related to prior exposure to study drug, the event should be reported through use of the Adverse Event eCRF.

An exception is made for Grade 3 and 4 infections (related and unrelated to prior study treatment), which should be reported until up to 2 years after the last dose of study treatment.

The Sponsor should also be notified of events of second malignancies indefinitely (related and unrelated to study treatment, even if the G+Atezo+pol treatment group or the overall study has been closed) for patients who received obinutuzumab.

If the EDC system is not available, the investigator should report these events directly to the Sponsor or its designee, either by faxing or by scanning and emailing the paper

Clinical Trial Serious Adverse Event/Adverse Event of Special Interest Reporting Form using the fax number or email address provided to investigators.

**5.7 EXPEDITED REPORTING TO HEALTH AUTHORITIES,
INVESTIGATORS, INSTITUTIONAL REVIEW BOARDS, AND
ETHICS COMMITTEES**

The Sponsor will promptly evaluate all SAEs and adverse events of special interest against cumulative product experience to identify and expeditiously communicate possible new safety findings to investigators, IRBs, ECs, and applicable health authorities based on applicable legislation.

To determine reporting requirements for single adverse event cases, the Sponsor will assess the expectedness of these events using the following reference document:

- Obinutuzumab Investigator's Brochure
- Atezolizumab Investigator's Brochure
- Polatuzumab Vedotin Investigator's Brochure
- Rituximab Investigator's Brochure

The Sponsor will compare the severity of each event and the cumulative event frequency reported for the study with the severity and frequency reported in the applicable reference document.

Reporting requirements will also be based on the investigator's assessment of causality and seriousness, with allowance for upgrading by the Sponsor as needed.

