6.6 EFFICACY ANALYSES

The primary and secondary efficacy analyses will include all patients enrolled in the expansion phase, and will be performed by treatment group. In addition, patients with FL who received polatuzumab vedotin at the RP2D during the dose-escalation phase will be pooled for analysis with patients with FL treated in the expansion phase. Patients with DLBCL from the safety run-in phase will be pooled for analysis with patients with DLBCL treated in the expansion phase at the same polatuzumab vedotin dose. A censoring will be applied as of 1 March 2018 to the efficacy analyses, to evaluate the effect of the triplet drug combination in each treatment group. The efficacy analysis will be performed on the censored efficacy dataset, and will include data from patients as of 1 March 2018 plus the corresponding assessment time window (see [Appendix 1](#) and [Appendix 2](#)).

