6.6.3 Exploratory Efficacy Endpoints

Exploratory efficacy analyses will include estimation of the proportion of patients achieving each of the following endpoints:

- For FL patients who have positive PET scans at EOI: CR at 12 months, as determined by the investigator on the basis of PET-CT scans

Point estimates will be presented, along with the corresponding two-sided 90% Clopper-Pearson exact CIs. Patients without a post-baseline tumor assessment will be considered non-responders.

OS will be summarized descriptively using the Kaplan-Meier method (Kaplan and Meier 1958). For the OS analysis, data for patients who have not died will be censored at the date the patient was last known to be alive. Where medians are reached, the corresponding estimated median will be provided, along with the 95% CI using the method of Brookmeyer and Crowley (1982).

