- ^c EOI assessments should be performed 6–8 weeks after Day 1 of the last induction cycle. As an exception, patients who discontinue induction treatment prematurely because of an adverse event may undergo EOI assessments 4–8 weeks after their last dose of study treatment.
- ^d Patients who complete treatment or prematurely discontinue treatment for reasons other than disease progression will undergo assessments at the 90-day safety follow-up visit.
- ^e Informed consent must be documented before any study-specific screening procedure is performed.

Appendix 1

Schedule of Assessments for Patients with Follicular Lymphoma (cont.)

- ^f Vital signs include respiratory rate, pulse rate, body temperature, and systolic and diastolic blood pressures while the patient is in a seated position. Record abnormalities observed at baseline on the General Medical History and Baseline Conditions eCRF. At subsequent visits, record new or worsened clinically significant abnormalities on the Adverse Event eCRF. For obinutuzumab infusions: For the first cycle, second cycle, and for patients who experience an infusion-related reaction, vital signs will be measured prior to the infusion, every 15 (\pm 5) minutes for the first 90 minutes of the infusion, and then every 30 (\pm 10) minutes until 1 hour after completion of the infusion. For subsequent cycles, vital signs will be measured every 30 minutes during the infusion, except in patients who had experienced an infusion-related reaction during a prior infusion. For polatuzumab vedotin infusions: During the administration of polatuzumab vedotin, vital signs should be assessed before the start of the infusion, every 15 (\pm 5) minutes during the infusion, at the end of the infusion, and every 30 (\pm 10) minutes for 90 minutes following completion of dosing at Cycle 1 and at Cycle 2, and 30 (\pm 10) minutes following completion of dosing in subsequent cycles.
- ^g Perform only in patients who will not be receiving maintenance treatment.
- ^h Includes evaluation of the head, eyes, ears, nose, and throat, and the cardiovascular, dermatological, musculoskeletal, respiratory, gastrointestinal, genitourinary, and neurological systems. Record abnormalities observed at baseline on the General Medical History and Baseline Conditions eCRF.

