- ee Includes CT scan of the neck (if clinically indicated), chest, abdomen, and pelvis. If contrast is medically contraindicated (e.g., patients with contrast allergy or impaired renal clearance), MRI scans of the chest, abdomen, and pelvis (and neck, if clinically indicated) and a non-contrast CT scan of the chest may be performed. Combined PET/CT scanners may be used to collect diagnostic CT scans, but only according to the technical guidelines in the imaging manual. The screening CT scan must be performed within 35 days prior to Day 1 of Cycle 1.

Appendix 1

Schedule of Assessments for Patients with Follicular Lymphoma (cont.)

- ^{ff} Perform within 7 days prior to Day 1 of Cycle 3, and at 12, 18, and 24 months after initiation of induction treatment, within 14 days prior to treatment administration. Patients with radiographic evidence of progression at the end of Cycle 2 who continue to receive study treatment per criteria defined in Section 3.1.1 should have a CT scan repeated 4–8 weeks later.
- ^{gg} Perform only if not done within the previous 3 months.
- ^{hh} Bone marrow biopsy and aspirate must be performed within approximately 3 months prior to Day 1 of Cycle 1.
- ⁱⁱ For patients with bone marrow involvement at screening, a repeat assessment will be performed at EOI if there is radiologic evidence of a complete response, and during maintenance or at EOM if there is radiologic evidence of a complete response or if clinically indicated (e.g., if there is clinical suspicion of progressive disease in the bone marrow with no radiologic evidence of progression).
- ^{jj} Refer to Sections 4.3.2.5 and Section 4.3.2 for details on dosing and schedule.
- ^{kk} *Patients who experience disease progression or discontinued study treatment will be evaluated for survival status and new anti-lymphoma treatment every 3 months until the end of the study. The end of the study is defined as the time when all enrolled patients with FL have completed or discontinued study treatment and all enrolled patients with DLBCL have been followed for at least 1 year after they have completed or discontinued study treatment.*

Appendix 2
Schedule of Assessments for Patients with Diffuse Large B-Cell Lymphoma

	Screening ^a		Induction (6 months; 21-day cycles)		EOI After Last Induction Dose ^b	90-Day Safety FU Visit (at 3 Months) ^c	Survival FU Period (Q3M) ^{ee}
	D -28 to D -1	D -14 to D -1	Cycle 1 (\pm 1 day)	Cycles 2–6 (\pm 2 days)			
			D1	D1			

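### The survival follow-up footnotes omit patients who complete treatment and stay progression-free, so later Kaplan-Meier OS would tend to be too low if they are applied as written

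*Combined protocol and SAP*

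**What the plan says.** Version 8 puts a survival follow-up period back into the schedules of assessments, running up to study closure. Its scope is set by Appendix 1 footnote kk (FL), repeated in Appendix 2 footnote ee (DLBCL): "Patients who experience disease progression or discontinued study treatment will be evaluated for survival status and new anti-lymphoma treatment every 3 months". The next sentence of each footnote says that the study ends when FL patients have completed or stopped treatment and "all enrolled patients with DLBCL have been followed for at least 1 year after they have completed or discontinued study treatment".

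Other relevant text:
- Appendix 1 footnote d and Appendix 2 footnote c, on the 90-day visit: "Patients who complete treatment or prematurely discontinue treatment for reasons other than disease progression will undergo assessments at the 90-day safety follow-up visit".
- Section 3.2 ends the study when every patient has "completed the 90-day safety follow-up visit, following completion or premature discontinuation of study treatment". It has no 1-year element. Section 8.5 uses the 1-year definition.
- Section 5.6: after the adverse event reporting period, "all deaths, regardless of cause, should be reported through use of the Long-Term Survival Follow-Up eCRF".
- Section 6.6.3: "OS will be summarized descriptively using the Kaplan-Meier method", and "data for patients who have not died will be censored at the date the patient was last known to be alive".
- Section 6.6: "A censoring will be applied as of 1 March 2018 to the efficacy analyses". It does not say whether OS is included.

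**The concern.** The protocol repeatedly treats completing and discontinuing treatment as two different states: in the second sentence of kk and ee, in Sections 3.1.5 and 3.2, and in the 90-day-visit footnotes. The first sentence of kk and ee names only discontinuation and progression. A patient who completes treatment and stays progression-free is therefore outside the quarterly checks as written, although the next sentence expects DLBCL completers to be followed for a year.

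Follow-up length then depends on outcome. Patients who progress or stop early are followed to the end of the study, while those doing best are last seen at the 90-day visit. Kaplan-Meier assumes that patients censored at a given time have the same future risk as those still followed, and here they would tend to have a lower one. Section 5.6 does not cure this: it brings in completers' deaths but does not move forward the dates of completers who are alive. The timing of new anti-lymphoma treatment is lost for the same patients.

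**Working it through.** The plan states no OS rate, event target or follow-up target, so there is no figure to reproduce.

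**When scheduled contact ends** (30.44 days per month)
- DLBCL, 6 cycles: last dose at 5 × 21 = 105 days; 90-day visit at 195 days = 6.4 months. One year after the last dose is 470 days = 15.4 months, so the gap is about 9 months.
- FL, full maintenance: Month 1 starts 8 weeks after Cycle 6 Day 1, at 105 + 56 = 161 days. The last dose, in Month 23, is at 161 + 22 × 28 = 777 days; the 90-day visit is at 867 days = 28.5 months. In a 4-year study the gap is at most 48 − 28.5 = 19.5 months.

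**How many DLBCL patients could be affected**

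Section 1.5.4.3 gives DLBCL median PFS of 1.9 months (obinutuzumab + polatuzumab 1.8 mg/kg, immature) and 5.6 months (rituximab + polatuzumab 2.4 mg/kg). These are neighbouring regimens, not this one. Induction lasts 126 days = 4.14 months. With exponential times:
- P(progression-free at 4.14 months) = exp(−ln 2 × 4.14 / 1.9) = 0.22, and 0.60 with a median of 5.6 months.
- Of 23 enrolled, that is about 5 to 14 patients.

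**Effect on 12-month DLBCL OS**

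I simulated exponential PFS plus exponential post-progression survival, with non-completers followed to 15.5 months. The documents give no post-progression survival; medians of 4 and 8 months are assumed, as is the intermediate PFS of 3.5 months.

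| Median PFS / post-progression survival (months) | Status known for all | Relapsed completers enter follow-up; others censored at 6.4 months | No completer re-enters; all censored at 6.4 months |
|---|---|---|---|
| 1.9 / 4 | 0.23 | 0.22 | 0.20 |
| 1.9 / 8 | 0.46 | 0.46 | 0.45 |
| 3.5 / 8 | 0.56 | 0.54 | 0.49 |
| 5.6 / 4 | 0.48 | 0.41 | 0.29 |
| 5.6 / 8 | 0.65 | 0.61 | 0.53 |

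The middle scenario applies the footnote's progression trigger and assumes that relapse is detected: bias 0 to 7 points. The last assumes that relapse after the end-of-induction scan goes unnoticed: up to 19 points.

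If no completer re-enters but completers' deaths are reported under Section 5.6, the estimate is 0.42 against 0.46 (1.9 / 8) and 0.47 against 0.65 (5.6 / 8). One-sided updating does harm even without a prognostic difference. With 30% completing and median survival of 6 months in both groups (after the last dose for completers), 12-month OS is 28.6% with full follow-up, 28.7% with completers censored at the 90-day visit, and 24.5% with only their deaths added.

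If every living completer attends the Appendix 4 visit at 15.4 months and deaths are reported, the 12-month bias is zero in every scenario.

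**FL, 36-month OS**

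Assumed: 30 to 70% complete; median survival 24 to 36 months in non-completers and 60 to 120 months after the last dose in completers. The estimate is 3 to 7 points low with completers censored at the 90-day visit, and 5 to 13 points low if only their deaths are added. No completer re-enters through progression here, so these are upper-end figures for those assumptions.

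DLBCL OS at 6 months and FL OS at 24 months are unaffected, because the gap has not begun.

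**The case against.** The strongest case is that the protocol already follows many of these patients, and that little depends on the rest.

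- **Completers who relapse are covered.** Progression is itself a trigger in kk and ee, and Section 4.5.6 requires a full tumor assessment whenever progression or relapse is suspected. A reader might infer that no completer ever enters survival follow-up; the documents do not support that. This point stands and brings the DLBCL range down to 0 to 7 points when relapse is detected. Detection is not assured: Appendix 2 schedules no scan after the end-of-induction assessment.
- **Later contacts exist.** Appendix 4 keeps a DLBCL sample 1 year after the last polatuzumab vedotin dose. It is not a survival check, but attendance gives an alive date. Version 8 removed that visit from Appendix 3, so FL completers have no equivalent. Both appendices also have a sample at 120 ± 30 days after the last dose, which moves last contact by at most about 2 months.
- **The 1-year sentence shows intent to follow DLBCL completers.** It does, and that makes this a contradiction to reconcile, not a deliberate exclusion. It does not tell a site whom to call, and it does not cover FL.
- **The data cut may make this moot.** Section 5.3.5.8 calls mortality an efficacy endpoint, and Section 6.6 exempts nothing. If the 1 March 2018 cut covers OS, the restored follow-up hardly enters the analysis.
- **Some DLBCL completers stopped later.** Before Version 7, responders could receive up to 8 months of consolidation, so 6.4 months applies only to those who ended at 6 cycles.
- **Low stakes.** OS is exploratory and descriptive in 36 patients, and the objective in Section 2.2.3 names only the FL regimen. At n = 23, in one assumed case (30% complete; medians 6 and 24 months), the SD of the 12-month estimate is about 10 to 13 points, larger than the 0 to 7 point bias.

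**Conclusion.** The gap is real and should be closed. As written, progression-free completers have no scheduled survival check after the 90-day visit, in conflict with the 1-year DLBCL follow-up in the same footnotes. The direction of any resulting bias is downward when completers survive longer than other patients, or when their deaths are collected without updating survivors.

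The size is conditional. For 12-month DLBCL OS it is about 0 to 7 points if relapsing completers are detected, and up to about 19 if they are not, given the PFS range above and an assumed 4 to 8 months of post-progression survival. It shrinks or disappears at 12 months if the Appendix 4 visit supplies alive dates, and is negligible if the 1 March 2018 cut covers OS. FL completers lack the one-year visit, but only OS beyond about 28.5 months is exposed.

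A reader might infer that OS in this study is biased downward as a matter of fact. The documents do not support that: it depends on literal application of the footnotes, on completion and relapse rates that they do not give, and on a data cut whose scope is unstated.

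**What to change.** 1. Reword kk and ee along these lines: *every patient who completes or stops study treatment, or who progresses, is checked for survival status and new anti-lymphoma treatment at 3-month intervals up to the end of the study.*
2. Reconcile the end-of-study definition in Section 3.2 (last 90-day visit) with kk, ee and Section 8.5 (1 year for DLBCL). Otherwise the reworded follow-up has no defined end.
3. State in Section 6.6 or 6.6.3 whether the 1 March 2018 cut applies to OS.
4. Before the OS analysis, update the last-known-alive date for every patient not known to have died who has not withdrawn consent, so that deaths and survivors are brought up to the same date.

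The cost is one sentence in each of two footnotes, two clarifications, and a few extra status checks among 36 patients. With survival status current for everyone, this source of bias is removed.

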Appendix 6 **Eastern Cooperative Oncology Group Performance Status Scale**

Grade	Description
0	Fully active Able to carry on all pre-disease performance without restriction
1	Restricted in physically strenuous activity but ambulatory and able to carry out work of a light or sedentary nature (e.g., light housework or office work)
2	Ambulatory and capable of all self-care but unable to carry out any work activities Up and about >50% of waking hours
3	Capable of only limited self-care; confined to a bed or chair >50% of waking hours
4	Completely disabled Cannot carry on any self-care Totally confined to bed or chair
5	Dead

Appendix 7

Ann Arbor Staging

Grade	Description
Stage I	Involvement of a single lymph node region (I) or of a single extralymphatic organ or site (IE) ^a
Stage II	Involvement of two or more lymph node regions or lymphatic structures on the same side of the diaphragm alone (II) or with involvement of limited, contiguous extralymphatic organ or tissue (IIE)
Stage III	Involvement of lymph node regions on both sides of the diaphragm (III), which may include the spleen (IIIS) or limited, contiguous extralymphatic organ or site (IIIE), or both (IIIES)
Stage IV ^b	Diffuse or disseminated foci of involvement of one or more extralymphatic organs or tissues, with or without associated lymphatic involvement

Note: All cases are subclassified to indicate the absence (A) or presence (B) of the systemic B symptoms of significant unexplained fever ($> 38^{\circ}\text{C}$), night sweats, or unexplained weight loss exceeding 10% of body weight during the 6 months prior to diagnosis.

^a The designation "E" generally refers to extranodal contiguous extension (i.e., proximal or contiguous extranodal disease) that can be encompassed within an irradiation field appropriate for nodal disease of the same anatomic extent. A single extralymphatic site as the only site of disease should be classified as IE, rather than Stage IV.

^b Involvement of bone marrow at screening will always qualify for Ann Arbor Stage IV and should be recorded as extranodal involvement.

Adapted from:

Appendix 8

Follicular Lymphoma International Prognostic Index

Table 1 Follicular Lymphoma International Prognostic Index

FLIPI Risk Factor	Number of FLIPI Risk Factors
Ann Arbor Stage III or IV	
Age >60 years	
Serum LDH >1 × ULN	
Anemia (hemoglobin <120 g/L)	
Involved nodal areas >4	
FLIPI Risk Group	Number of FLIPI Risk Factors
Low	0 or 1
Intermediate	2
High	3 to 5

FDG=fluorodeoxyglucose; FLIPI=Follicular Lymphoma International Prognostic Index; PET=positron emission tomography; ULN=upper limit of normal.

Note: The results of FDG-PET should not be taken into account for calculation of FLIPI since this prognostic score was established without FDG-PET.

Adapted from: Solal-Celigny P, Roy P, Colombat P, et al. Follicular lymphoma international prognostic index. *Blood* 2004;104:1258–64.

Table 2 Follicular Lymphoma International Prognostic Index 2

FLIPI2 Risk Factor	Number of FLIPI2 Risk Factors
Bone marrow involvement	
Age >60 years	
β ₂ microglobulin >1 × ULN	
Anemia (hemoglobin <120 g/L)	
Longest diameter of largest involved node >6 cm	
FLIPI2 Risk Group	Number of FLIPI2 Risk Factors
Low	0
Intermediate	1 or 2
High	3 to 5

FDG=fluorodeoxyglucose; FLIPI2=Follicular Lymphoma International Prognostic Index 2; PET=positron emission tomography; ULN=upper limit of normal.

Note: The results of FDG-PET should not be taken into account for calculation of FLIPI2 since this prognostic score was established without FDG-PET.

Adapted from: Federico M, Bellei M, Marcheselli L, et al. Follicular Lymphoma International Prognostic Index 2: a new prognostic index for follicular lymphoma developed by the International Follicular Lymphoma Prognostic Factor Project. *J Clin Oncol* 2009;27:4555–62.

Appendix 9 **Anaphylaxis Precautions**

EQUIPMENT NEEDED

- Tourniquet
- Oxygen
- Epinephrine for subcutaneous, intravenous (IV), and/or endotracheal use in accordance with standard practice
- Antihistamines
- Corticosteroids
- IV infusion solutions, tubing, catheters, and tape

PROCEDURES

In the event of a suspected anaphylactic reaction during study treatment infusion, the following procedures should be performed:

- Stop the study treatment infusion.
- Apply a tourniquet proximal to the injection site to slow systemic absorption of study treatment. Do not obstruct arterial flow in the limb.
- Maintain an adequate airway.
- Administer glucocorticoids, antihistamines, epinephrine, or other medications as required by patient status and directed by the physician in charge.
- Continue to observe the patient and document observations.

Appendix 10

Preexisting Autoimmune Diseases

Patients should be carefully questioned regarding their history of acquired or congenital immune deficiencies or autoimmune disease. Patients with any history of immune deficiencies or autoimmune disease listed in the table below will be excluded from participating in the study. Possible exceptions to this exclusion could be patients with a medical history of such entities as atopic disease or childhood arthralgias where the clinical suspicion of autoimmune disease is low. Patients with a history of autoimmune-related hypothyroidism on a stable dose of thyroid replacement hormone may be eligible for this study. In addition, patients with transient autoimmune manifestations of an acute infectious disease that resolved upon treatment of the infectious agent are not excluded (e.g., acute Lyme arthritis). Please contact the Medical Monitor regarding any uncertainty over autoimmune exclusions.

Acute disseminated encephalomyelitis	Dermatomyositis	Neuromyotonia
Addison's disease	Diabetes mellitus type 1	Opsoclonus myoclonus syndrome
Ankylosing spondylitis	Dysautonomia	Optic neuritis
Antiphospholipid antibody syndrome	Epidermolysis bullosa acquista	Ord's thyroiditis
Aplastic anemia	Gestational pemphigoid	Pemphigus
Autoimmune hemolytic anemia	Giant cell arteritis	Pernicious anemia
Autoimmune hepatitis	Goodpasture's syndrome	Polyarteritis nodusa
Autoimmune hypoparathyroidism	Graves' disease	Polyarthritis
Autoimmune hypophysitis	Guillain-Barré syndrome	Polyglandular autoimmune syndrome
Autoimmune myocarditis	Hashimoto's disease	Primary biliary cirrhosis
Autoimmune oophoritis	IgA nephropathy	Psoriasis
Autoimmune orchitis	Inflammatory bowel disease	Reiter's syndrome
Autoimmune thrombocytopenic purpura	Interstitial cystitis	Rheumatoid arthritis
Behcet's disease	Kawasaki's disease	Sarcoidosis
Bullous pemphigoid	Lambert-Eaton myasthenia syndrome	Scleroderma
Chronic inflammatory demyelinating polyneuropathy	Lupus erythematosus	Sjögren's syndrome
Chung-Strauss syndrome	Lyme disease - chronic	Stiff-Person syndrome
Crohn's disease	Meniere's syndrome	Takayasu's arteritis
	Mooren's ulcer	Ulcerative colitis
	Morphea	Vitiligo
	Multiple sclerosis	Vogt-Kovanagi-Harada disease
	Myasthenia gravis	Wegener's granulomatosis
	Myasthenia gravis	

Appendix 11

Calculation of Creatinine Clearance Using the Cockcroft-Gault Formula

$$\text{Creatinine clearance (men)} = \frac{(140 - \text{Age}) \times \text{Lean body weight (kg)}}{\text{Serum Creatinine (mg/dL)} \times 72}$$

$$\text{Creatinine clearance (women)} = \frac{0.85 \times (140 - \text{Age}) \times \text{Lean body weight (kg)}}{\text{Serum Creatinine (mg/dL)} \times 72}$$

Adapted from: Gault MH, Longerich LL, Harnett JD, et al. Predicting glomerular function from adjusted serum creatinine [editorial]. *Nephron* 1992;62:249–56.
